7.2.3 Study Stopping Rule Guideline

The following should serve as a general guide for the DSMB to recommend stopping the enrolment and/or further drug administration in the study for safety reasons. This is in addition to the stopping rule based on the futility analysis (already performed) outlined in Section 12.7.2. Other considerations may be used to arrive at such decisions, which must involve Laurent Pharmaceuticals Executive Management. Taking in consideration the sizeable proportion of these at-risk patient population to develop severe complications, including death from COVID-19 disease:

- Occurrence of any case of death that is attributable to fenretinide (in such a case, the blind will have to be broken and allocated treatment identified);
- Occurrence of an increased number, relative to placebo, of unexpected SAEs that could be attributable to the drug (at least *probable* causality relationship) that raise the DSMB/Investigators concerns about patients' safety.

7.3 Blinding and Randomization

Given the potential for bias in the interpretation of the study endpoints, the RESOLUTION study must be placebo-controlled, double-blinded, and randomized in order to obtain sufficiently robust data and provide key information in the design of subsequent well controlled clinical trials of LAU-7b in the treatment of COVID-19 disease.

7.3.1 Rationale for Placebo Control

It is appropriate that this study be placebo-controlled since there is no consensual effective treatment at this point in time. In this pandemic circumstance where search for a treatment of COVID-19 disease is extreme, participation in this study will not exclude co-administration with new SOC treatments, as they become available (for example remdesivir and dexamethasone). This will be evaluated on a case-by-case basis. However, co-enrolment in other interventional studies of unproven COVID-19 treatments is not permitted. A placebo control is suitable and will permit to have unbiased assessment of the study variables. It is essential to maintain the patients on their standard of care for other health conditions, assuming this meets all inclusion/exclusion criteria.

7.3.2 Blinding and Breaking the Blind

This is a double-blind study. Patients, Investigators and Site Staff, sponsor and CRO personnel, and data managers will be kept blinded to treatment assignments until the end of the study, except for emergency unblinding as described below.

Only the Clinical Trial Material manufacturer's and Packaging/Distribution provider's unblinded personnel, duly identified members of the CRO managing the study as well as the staff coordinating the interactive web response system (IWRS) will be knowledgeable of individual treatment assignments. As well, in the case of emergency unblinding as described below, some additional people will become aware of treatment assignment for specific patient(s).

The study blind may be broken for an individual patient or several patients in the event of an emergency in which knowledge of the treatment assignment is needed for the safety of the patient(s) and/or for medical decision-making or as required by local regulatory authority. Unless the event for which the blind needs breaking is life threatening, the investigator should first contact the CRO's medical monitor (or designee) prior to breaking the blind.

The investigator will obtain unblinding information by accessing the IWRS system. The reason and justification for breaking the blind must be fully documented in the source documentation and captured on the patient(s) electronic case report form (e-CRF).

7.3.3 Randomization Scheme and Stratification

Computer-generated randomization sequences will be programmed into the IWRS. At the time of Randomization, not before, the IWRS will assign a Subject number (Randomization Number) to each patient. Randomization will be stratified by clinical site and randomized in a 1:1 double-blinded fashion to either LAU-7b (active) group or the placebo (control) group. Stratification by clinical site is appropriate when each site is expected to randomize a sizeable number of patients; this will enable an even distribution of patients among the two treatment groups, by site. Detailed instructions for randomization will be provided separately.

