5.4.3.3 Rationale for Study Assessments

The study assessments are generally part of the SOC for patients hospitalized for suspected or confirmed SARS-CoV-2 infection with the presence of underlying conditions or measurement associated with a greater risk of complications. Most are frequently assessed during hospitalization and includes vital signs, symptom check, safety laboratory tests, assessing the need or not for supplemental oxygenation or for a transfer to the intensive care unit (ICU), as well as determining if hospitalization can end (patient discharge). It is recognized that during the pandemic, institution/departmental policies for preventative reasons can change very rapidly and affect the hospitalization thresholds.

EQ-5D-5L Quality of Life questionnaire: This questionnaire is a well-documented scoring system that have been widely used and validated as QoL assessment tool for this type of population. It will be filled at screening and by fully eligible patients (confirmed SARS-CoV-2 infection) reaching Days 14, 29 and 45 (and at the longer term safety/QoL assessment, around 2 months after study start), and able to fill the questionnaire. This is not part of Standard of Care, but this is relevant for outcomes since patients with varying degrees of functionality will represent a variable pharmacoeconomic weight.

Scoring the Heath Status of the patients using the ordinal scale: Performed on specific days by the study coordinators or other delegated and trained staff, this assessment aims at formally determine in which category the patient is, each period of 24 hours (a study Day) once at a time. This is not done as part of SOC, but is key for this study. Several variables are derived from it.

Serial oropharyngeal swabs to detect SARS-CoV-2 virus: This was an optional objective measurement of the virus presence and allows to determine how long the virus shedding lasts from the oropharyngeal cavity. Unfortunately, none of the clinical sites volunteered to perform it due to the complexity of accessing repeatedly the patient on the COVID wards and the lack of resources. This assessment will not be pursued in the expansion of the study.

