7.2 Study Overview

7.2.1 Description

RESOLUTION is a multicentre, randomized, double-blind (patients, Investigators and blinded study staff), placebo-controlled Phase II study of LAU-7b for the treatment of COVID-19 disease in patients at a higher risk than the general COVID-19 disease population to develop complications while hospitalized.

To be eligible for the study, patients must be symptomatic of COVID-19, confirmed by PCR (or alternates but excluding rapid antigen tests)) to have a SARS-CoV-2 infection, be aged 18 years and above, and meet all other study inclusion and none of the exclusion criteria at screening. There is no time limit between the onset of symptoms or the confirmation of SARS-CoV-2 infection and screening.

Eligible patients will be randomized 1:1, at each clinical site, to either LAU-7b (active) group or placebo (control) group. After randomization, patients will enter the treatment phase of the study. There will be no active control treatment but patients will undergo the COVID-19 disease SOC at their institution.

Since the study randomizes only confirmed cases of SARS-CoV-2 infection, the screen failure rate is very low. It is estimated that based on sample size calculation using the effect size observed in the pilot portion of the study for the revised Primary Efficacy Endpoint in the subset of patients with Health Status score 3 or 4 at baseline, up to a total of approximately 264 patients with a Health Status score 3 or 4 at baseline will be recruited in the expansion. Patients will be enrolled at approximately 25-30 centers in the United States of America and in Canada. The study treatment (LAU-7b or matching placebo) will be administered once a day in the fed state (with the main meal of the day if possible) for up to 14 days on treatment.

Patients will be evaluated at pre-specified times during and after the study treatment period, for efficacy, safety, as well as for Quality of Life.

This design is appropriate for this phase of development (confirmatory Phase 3 portion) and will ensure that the highest quality of data is collected with minimal bias and the patient's safety and wellbeing are preserved. A Data and Safety Monitoring Board (DSMB) is monitoring this study.

The overall study structure for Health Status 3+4 patients in the Phase 2 pilot and the Phase 3 extension is presented below in Figure 2.

[figure not shown]

Figure 2: Overall structure of the study

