9.2.3 In-Hospital Days

For this study in hospitalized patients with confirmed COVID-19 disease, the hospital stay duration will vary as a function of complications/improvement observed with each given patient, the bed and resources availability, rules and restrictions imposed by Health Authorities (Institution, Governmental...etc.). In order to minimize the burden of this study on the hospital resources, the in-hospital study requirements will piggyback on the SOC, with some exceptions. The overall scheme can be found in the Schedule of Event on page 11. Details are presented below.

1. Pre-Dose on Day 4 only:

If the patient has tolerated the Initial treatment of 3 days, if not done previously, a replenishment will be requested in the IWRS and the Follow-up treatment container (22 capsules) will be retrieved from the pharmacy (where applicable) and stored in the ward's refrigerator.

- 2. On Days 5, 8 and 12 (visits 5, 8 and 12, with a window of +/- 1 day while in hospital), the following assessments will be done:
 - a. Concomitant medication verification, including any supplemental oxygen currently in use;
 - b. Directed physical examination (symptom- and disease-driven);
 - c. From SOC, collect the vital signs including heart rate, respiratory rate, oxygen saturation and body temperature (can be done multiple times during each day as part of SOC, but at a minimum twice);

- d. COVID-19 symptom check (including but not limited to, fever, myalgia, coughing, dyspnea, smell and taste alteration, headache, gastrointestinal disorders...etc.) as per SOC;
- e. SOC laboratory tests including at a minimum, urinalysis (dipstick), hematology and serum chemistry, as per Section 11.2 (the laboratory test can be performed within +/- 1 day from the target visit day);
- f. Health status determination using the 7-point ordinal scale;
- g. Handing study medication for intake during the main meal of the day;
- h. Asking safety-focused open-ended questions:
 - i. How is your health today?
 - ii. How is your vision today?
 - iii. How is your skin today?
- i. Adverse event verification and follow-up on ongoing adverse events.

3. On Day 14 or on the Day of hospital discharge (not a preset visit number), the following assessments will be done:

- a. Concomitant medication verification, including any supplemental oxygen currently in use;

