12 STATISTICAL ANALYSIS

A statistical analysis plan (SAP) will provide details of the methods of analysis to address all study objectives. The SAP may be amended during the course of the study, but will be finalized before the cutoff date for any analysis, interim or final.

Data summaries by treatment group will be presented. For categorical data such as the 7-point Ordinal Scale, data will be tabulated in frequency tables to display the number and proportion of patients for each category by treatment group. For continuous variables, data will be summarized with the number of patients, mean, standard deviation, median, and minimum and maximum values by treatment group. Baseline assessments for each outcome variable will be defined as the screening measurement unless a repeat value was obtained, see restrictions in Section 9.2.1.1, before the first dose of study drug. Statistical significance will be set at the 5% level (one-sided) for the pilot portion and at the 5% level (two-sided) for the extension. Consideration

will be given for adjusting for pre-specified prognostic baseline factors such as age, the ordinal scale health status at baseline and comorbidities, where applicable.

Diligent efforts will be made to prevent missing data in the study. For example, patients who discontinue the study treatment early should still be followed for all regularly scheduled visits for safety and relevant efficacy assessments, until the Day 60 follow-up. A clear distinction should be made between treatment discontinuation and study withdrawal. Efficacy assessments occurring after treatment discontinuation should not be included in the per-protocol analysis.

Database lock and statistical analyses will be performed for the pilot portion and the extension, separately.

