12.7.2 Analysis of Secondary Efficacy Endpoints

Pre-defined Clinical Parameters:

- The ordinal scale will be used to estimate a proportional odds model. The primary hypothesis test will be based on a test of whether the common odds ratio for treatment is equal to one. The model fit using a goodness-of-fit likelihood ratio test will be evaluated. The distribution of severity results will be summarized by treatment arm as percentages. The validity of the proportionality assumption will be evaluated and tested. Participants without final outcome data will be excluded from the analysis. Sensitivity analyses will evaluate the impact of making different assumptions about missing observations. These sensitivity analyses will be fully defined in the SAP.
- Count data variables: The number of days of hospitalization, the number of days in ICU, the number of days under mechanical ventilation...etc., will be tabulated by treatment and compared with an appropriate count data model, e.g., ANOVA model (if assumptions of normality and homogeneity of variance appear acceptable), Poisson regression, negative binomial regression, zero-inflated regression, etc., depending on their distribution.
- Time to event data variables: The time to mechanical ventilation, time to recovery, time to aggravation (worsening by one category on the ordinal scale), and time to death will be tabulated by treatment and compared using a Cox proportional hazards model. If the proportional hazards assumption is violated, a stratified analysis will be conducted using stratified Cox regression. Additionally, Kaplan-Meier methods will be used to produce graphical presentations of the survival (aggravation-free survival, survival) by treatment group and to estimate cumulative aggravation-free survival and survival rates by treatment group.
- Change in ordinal scale at specific time points will be summarized by proportions (e.g., proportion who have a 1-, 2-, 3-, or 4-point improvement or 1-, 2-, 3-, 4-point worsening).
- Mean change-from-baseline for the ordinal scale will be analyzed through time, using a mixed model repeated measure (MMRM) model.
- Body weight and BMI changes from screening will be summarized using descriptive statistics by treatment and compared between treatments using an analysis of covariance (ANCOVA) with treatment as fixed effect; and adjustment for screening Ordinal Scale Health Status, and weight or BMI at baseline as covariates.

Formal Futility Analysis (Pilot Portion):

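### Randomization is stratified by site, but no secondary model in the supplied documents includes site; if discharge practice differs between sites, the discharge-driven endpoints lose some power

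*Protocol*

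**What the plan says.** **Randomization.** Protocol 7.3.3: "Randomization will be stratified by clinical site and randomized in a 1:1 double-blinded fashion". No other stratification factor is named, and no block size is given. Section 7.2.1: "Patients will be enrolled at approximately 25-30 centers in the United States of America and in Canada".

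**Site and hospital stay.** Section 9.2.3 says "the hospital stay duration will vary as a function of complications/improvement observed with each given patient, the bed and resources availability" and goes on to institutional and governmental rules. Section 5.4.3.3 says that "institution/departmental policies for preventative reasons can change very rapidly and affect the hospitalization thresholds".

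**Secondary models (12.7.2).**
- Ordinal status: "The ordinal scale will be used to estimate a proportional odds model", with no covariates stated.
- Times to event: "tabulated by treatment and compared using a Cox proportional hazards model", with a stratified Cox model if proportional hazards fails. The strata are not named.
- Days in hospital: ANOVA or a count model chosen on the distribution, with no covariates stated.
- Mean ordinal change: a mixed model for repeated measures, with no covariates stated.
- Weight, BMI and EQ-5D-5L: ANCOVA with covariates listed, site not among them.

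The general statement in Section 12 is that consideration "will be given for adjusting for pre-specified prognostic baseline factors such as age, the ordinal scale health status at baseline and comorbidities". The SAP addendum does not mention site and refers to the SAP of 29SEP2023 for the full description.

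**The concern.** On the 7-point scale, the line between categories 2 and 3 is the line between being out of hospital and in it. Time to recovery (endpoint 11) and duration of hospitalization (14) are therefore largely discharge decisions. Status on Days 14 and 29 (8), mean ordinal change (9) and one-category improvement (10) depend on discharge in part: a patient at 3 improves by going home, a patient at 4 by coming off oxygen.

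Stratifying by site balances the arms within each site, which removes site differences from the true sampling error of the treatment comparison. A model that ignores site does not credit this. In a linear model the between-site variation stays in the residual, so the reported standard error is too large. In Cox and proportional-odds models, omitting a prognostic factor pulls the treatment effect toward zero. At stake are the precision and the reported size of effects on endpoints meant to support the primary result.

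**Working it through.** **The plan's own figure.** The only power statement is for the primary endpoint: 264 patients, 7% vs 0%, two-tailed Fisher test, at least 90% power. With no events in the active arm and 132 per arm, 6 placebo events give p = 0.029 and 5 give p = 0.060, so 6 are needed. P(X ≥ 6) for X ~ Bin(132, 0.07) is 90.6%. The figure reproduces. No secondary endpoint has a stated power, so what follows rests on assumptions.

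**Inputs from the protocol.** N = 264, 1:1, two-sided 5%, 25-30 sites. Patients per site: 264/30 = 8.8 to 264/25 = 10.6, or about 9-11.

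**Assumed.** Intraclass correlation (ICC), between-site SD, blocks of 4, unequal site sizes, and effect sizes.

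**Linear models.** With balance within site, reported SE / true SE is r = 1/√(1 − ICC). True type I error is 2[1 − Φ(1.96r)]. If the site-adjusted test has power 1 − β, the unadjusted test has Φ(1.96 + z(1−β) − 1.96r). Degrees of freedom spent on site are ignored.

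| ICC | r | Type I error | Power when adjusted = 90% | when adjusted = 80% |
|---|---|---|---|---|
| 0.01 | 1.005 | 0.049 | 89.8% | 79.7% |
| 0.05 | 1.026 | 0.044 | 89.1% | 78.5% |
| 0.10 | 1.054 | 0.039 | 88.0% | 76.9% |
| 0.20 | 1.118 | 0.028 | 85.3% | 72.9% |

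Simulation with 27 sites and site as fixed effects agrees: power 88.1% vs 89.5% at ICC 0.10, and 84.9% vs 89.5% at 0.20.

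**Cox, shared frailty.** Check of the starting point: if all 264 recover, expected Z = ln(HR)·√264/2. At HR 1.5 this is 0.405 × 8.12 = 3.29, so power is Φ(3.29 − 1.96) = 91%. Two simulation runs (27 unequal sites, HR 1.5; 600 and 300 replicates) gave:

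| Site SD (log hazard) | No site | Shared frailty |
|---|---|---|
| 0 | 91% | 91% |
| 0.3 | 87-89% | 89-91% |
| 0.5 | 74-82% | 86-89% |

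Monte Carlo error is about 1.3 to 2.5 points per entry. The spread without site at SD 0.5 is wider than that comfortably explains, so the ranges are approximate. In the 600-replicate run the mean log HR without site fell from 0.41 to 0.35 at SD 0.5. Type I error with frailty was between about 0.035 and 0.06 across the two runs.

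**Full site strata.** Log-rank test, 28 unequal sites, 3,000 replicates, site SD 0 / 0.3 / 0.5 / 0.7:
- HR 1.5: ignoring site 89 / 87 / 82 / 72%; stratified 82 / 84 / 83 / 83%.
- HR 1.35: ignoring site 67 / 63 / 54 / 47%; stratified 58 / 58 / 58 / 60%.

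Full strata lose power at SD 0.3 or below. A separate Cox simulation (log HR 0.40, site SD 0.6) shows the mechanism: the SE is 0.126 without site and 0.140 with strata, while the estimate is 0.33 without site and 0.40 with strata.

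**Logistic (stand-in for proportional odds).** Site SD 0.4 and 0.8: power 86% vs 86% and 80% vs 83% (without vs with site). The estimate without site is 0.78 and 0.72 against a true 0.80.

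**Poisson.** Site SD 0.3: reported SE / true SD is 0.95-0.96 without site, and power is 81% either way. There is no conservatism and no power loss.

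**The case against.** **The main SAP may settle it.** Section 12 leaves methods to the SAP, and 12.7.2 reads as a summary that gives no covariates at all for several models. The covariate list in Section 12 is introduced as examples, so it is not closed. A reader might infer that the trial's final analysis omits site; the supplied documents show only that they do not include it. This objection stands in full.

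**The size is unknown.** No between-site variance is given. Section 9.2.3 puts the patient's own course first and site conditions after it, so a reader who concludes that site policy drives hospital stay goes further than the text. Section 5.4.3.3 also says policies change quickly, and a fixed site effect would not capture that. This stands as a limit on magnitude.

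**Leaving site out is defensible with 9-11 patients per site.** Against full strata this is right, as the log-rank figures show. It does not hold against a random effect, which cost nothing in the simulations when sites did not differ.

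**The error is in the safe direction.** In the linear, Cox and logistic simulations the tests without site were conservative or close to nominal. In the Poisson model the rate was slightly above nominal (0.064). The point concerns power and attenuated estimates, not false positives.

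**Conclusion.** The point holds as a modest one. Site is the sole stratification factor, the protocol itself gives a reason why it could affect hospital stay, and no secondary model in the supplied documents includes it. If sites differ, endpoints 8-11 and 14 lose power: about 1 to 5 points in linear models at ICC 0.05 to 0.20 (from 90%), and in Cox about 2-3 points at site SD 0.3 and 7-12 points at SD 0.5, compared with shared frailty. With no site differences nothing is lost. All these sizes rest on assumed variances, site sizes and hazard ratio.

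A reader might infer that standard errors are too large in every secondary model. That is the main mechanism only in the linear models. In Cox and proportional odds the loss comes mainly from shrinkage of the effect, and full adjustment raises the standard error. For Poisson the claim fails. Nor do the documents tie site practice to weight or EQ-5D-5L. The primary test is unaffected.

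**What to change.** First confirm whether the SAP of 29SEP2023 includes site. If it does not:

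- For endpoints 8-11 and 14, fit clinical site as a random effect (shared frailty in Cox; random intercept in the ordinal, count and mixed models), with baseline Health Status (3 vs 4) as a covariate.
- Do not use full site strata at about 9-11 patients per site.
- Name the strata for the Cox fallback in 12.7.2.
- The addendum puts the first release of results at 14MAR2024, so report these as a labelled site-adjusted sensitivity analysis and do not replace the planned secondary models.
- Leave the primary test unchanged. About 132 × 0.07 = 9 expected events carry no useful site information.

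The cost is a paragraph in the addendum and some model code, with little or no power loss if sites do not differ.
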